1.3. SCHEDULE OF EVENTS

Table 1: Schedule of Events for Phase 1 (Parts A and B)

Procedure	Screening Period Within 28 Days prior to first dose	Treatment Period							Follow-up Period		Notes
		PK Lead-in ^a	Cycle 1 (21 days)			Cycle 2 (21 days)		Cycles ≥ 3 (21 days)	Safety Follow-up ^b	Survival Follow-up	
		Day -3	Day 1	Day 8 (± 1 day)	Day 15 (± 3 days)	Day 1 (± 3 days)	Day 8 (± 3 days)	Day 1 (± 3 days)	30 (+3) days after last dose		
EGFR C797S status (pre-screening informed consent)	See Notes										Only if central pre-screening done. Can be done any time prior to screening.
Written informed consent (main study)	X										To be obtained prior to any study related procedures.
Review inclusion / exclusion criteria	X										All patients in Part A2 and B must have documented C797S EGFRmt. See Section 4.1 and Section 4.2
Demographics/ Medical history	X										Including prior antitumor treatment
Physical examination	X	X	X	X		X		X	X		Within 24 hours prior to dosing. May be symptom directed during treatment period. Examination of skin should be performed at each timepoint. See Section 7.1
Ophthalmological examination	X	As clinically indicated							X		See Section 7.1.5
Height and weight	X	X	X			X		X	X		Height at screening only
Vital signs	X	X	X	X	X	X	X	X	X		Heart rate, blood pressure, and body temperature. See Section 7.1
Hematology	X	X	X	X	X	X	X	X	X		Assessment prior to first day of dosing may be done up to 72 hours prior to dosing

											(Section 7.1.4) All other assessments may be done within 24 hours prior to dosing See Section 7.1
Chemistry	X	X	X	X	X	X	X	X	X		Assessment prior to first day of dosing may be done up to 72 hours prior to dosing (Section 7.1.4) All other assessments may be done within 24 hours prior to dosing See Section 7.1
Coagulation	X	X	X			X		X	X		Assessment prior to first day of dosing may be done up to 72 hours prior to dosing (Section 7.1.4) All other assessments may be done within 24 hours prior to dosing See Section 7.1
Urinalysis	X	X	X			X		X	X		Assessment prior to first day of dosing may be done up to 72 hours prior to dosing (Section 7.1.4) All other assessments may be done within 24 hours prior to dosing. See Section 7.1
Pregnancy test	X	X	(X)			X		X			For WOCBP only: Serum pregnancy test required at screening only. See Section 7.1 (X) not required for patients in Part A1

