Adverse events	X	X	X						X	(X)	From signing ICF through 30-day safety follow-up or until start of new anticancer therapy, whichever is earlier. See Section 10.1 (X) only related SAE Investigator becomes aware of
Concomitant medications	X	X	X						X		From signing ICF through 30-day safety follow-up or until start of new anticancer therapy, whichever is earlier. See Section 6.4
ECOG Performance Status	X		X			X		X	X		

PK sampling		See Table 13 / Table 14									Table 13 for QD dosing / Table 14 for BID
Central ECG		See Table 13 / Table 14									To be performed as triplicates. For patients in Part A1 only. See Section 7.1.2
Local ECG ^c	X		X			X		X	X		12-lead ECG. Not needed if central ECG done the same day. Additional ECG monitoring as clinically indicated. See Section 7.1.2
Echocardiography/ MUGA	X							X			From Cycle 4 onwards, every 4 cycles or as clinically indicated. See Section 7.1.3
cfDNA blood samples			X			X		X	X		From Cycle 3 onwards, every other cycle. After 12 months, every 3 cycles.
Tumor tissue samples	X					(X)			(X)		Baseline sample optional for patients in Part A1. See Section 11.2 (X) On-treatment biopsy optional; can be done at one of these timepoints
Radiologic tumor assessment	X		X						(X)	(X)	Every 6 weeks (±7 days) from C1D1 irrespective of cycle. After 12 months, every 9 weeks (±7 days). (X) Patients who discontinue study treatment without radiographic PD will continue every 9 weeks (±7 days) until radiographic PD. See Section 7.1
Survival status										X	Every 3 months (±2 weeks); collect also further anticancer therapies. See Section 7.1 . For patients in Part A2 and B only
Administration of TAS3351		X	X								Continuous dosing See Section 6.1

^a PK lead-in period applies to Part A1 only: During PK lead-in period, patients will receive a single dose of TAS3351 3 days prior to the start of multiple TAS3351 dosing in Cycle 1 with subsequent PK blood collection. The PK blood sample collection times during the PK lead-in period may be found in [Table 13](#). For these patients, 72-hour post-dose assessments occur on C1D1, prior to C1D1 dosing.

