9.2. Efficacy Endpoints

Efficacy endpoints based on radiographic imaging will be assessed per RECIST 1.1; endpoint definitions are summarized in [Table 15](#).

Table 15: Efficacy Endpoint Definitions

Endpoint	Definition
ORR	Proportion of patients experiencing a best overall response of PR or CR (per RECIST v1.1). Intracranial ORR be assessed based on ORR of CNS lesions only
DoR	Time from the first documentation of response to the first documentation of objective tumor progression or death due to any cause, whichever occurs first. Intracranial DoR be assessed based on DoR of CNS lesions only
DCR	Percentage of patients who have achieved a CR, PR, or stable disease (SD)
PFS	Time from date of first dose to the date of documentation of disease progression, or date of death, whichever occurs first
OS	Measured from the date of first dose until the date of death due to any cause

Abbreviations: CNS=central nerve system; CR=complete response; DCR=disease control rate; DoR=duration of response; ICR=independent central review; ORR=objective response rate; OS=overall survival; PFS=progression-free survival; PR=partial response; RECIST=Response Evaluation Criteria in Solid Tumors; SD=stable disease

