4. STUDY PERIODS, TREATMENT REGIMENS, AND POPULATIONS FOR ANALYSIS

4.1. Study Periods for Analyses

Study periods are defined in [Table 2](#).

Table 2: Definition of Study Periods for Analysis

Period	Definition
Study Period	From the day of the first ICF signature to the last day of Survival Follow-up Period
Screening Period	From the day of informed consent form (ICF) signature (up to 28 days before first dose) to the day before the first dose
Treatment Period	From the date of first dose of study drug (Day 1/PK lead-in for part A1) to the last day of dosing.
Safety Follow-up Period	30 (+3) days after the last day of dosing
Survival Follow-up Period	From the last day of Safety Follow-up period to death, or study completion, whichever happens first

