5.5.6. Progressive Free Survival (PFS)

Table 6: Event and Censoring Rules for PFS

Event/Censor	Decision	Date of event or censor to consider for analysis
Documented first disease progression	Event	Date of 1st PD scan
Death without disease progression	Event	Date of Death
Patients who not known to have progressed or died at the time of data cut-off	Censor	Date of last evaluable tumor scan (non-NE)
Patient progresses or dies immediately after two or more consecutive missed visits	Censor	Date of last evaluable tumor scan prior to the two missed visits (non-NE)
No baseline or post-baseline tumor assessment unless they die within two visits of baseline (<12 weeks from baseline)	Censor	Date of the first dose

For missing data, i.e., patients who were not known to have progressed or died at the time of data cut-off or who were progressed or died after 2 or more consecutive missed visit, the PFS will be censored at the date of last evaluable tumor scan. If no tumor assessments are performed unless patients die within two visits of baseline visit, PFS will be censored at the time of the first administration.

Secondary Analysis in Part A (Patients in part A2 only), B

The Kaplan-Meier method will be used to estimate the median and percentile with the 2-sided 95% CI calculated using the Brookmeyer and Crowley method.

Kaplan-Meier plot will be provided.

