7. DEFINITIONS AND CONVENTIONS FOR DATA HANDLING

7.1. Baseline Period

Baseline evaluations or events will be defined as evaluations or events that occur before the date and time of the first dose of study drug. Evaluations on the same date and time of the first dose of study drug will be considered as baseline evaluations.

In cases where the time (onset time of event or evaluation time and dosing time) is missing or not collected, the following definitions will apply:

- Pre-treatment AEs will be defined as AEs with an onset date prior to but not including the day of the first dose of study drug
- Baseline evaluations will be defined as evaluations with a date on or prior to the day of first dose of study drug

If there are multiple valid assessments, the assessment that is closest to the day (and time if collected) of the first dose of study drug will be used as the baseline in the analyses. If multiple assessments are collected on the same date (and time, if collected), the assessment with the latest database entry date (and time, if collected) will be considered as baseline.

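### The PFS exception for early deaths without a scan runs 12 weeks from baseline instead of from first dose, so some deaths after at most one missed scan can be censored at Day 1

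*SAP*

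**What the plan says.** The protocol (Section 9.2, Table 15) defines PFS as "Time from date of first dose to the date of documentation of disease progression, or date of death, whichever occurs first", and SAP Table 4 defines it the same way. Tumor scans are due "Every 6 weeks (±7 days) from C1D1 irrespective of cycle" (Protocol Section 1.3, Table 1).

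Three parts of SAP Section 5.5.6 decide what happens to an early death without a scan:

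- The last row of Table 6 censors at the date of first dose when there is "No baseline or post-baseline tumor assessment unless they die within two visits of baseline (<12 weeks from baseline".
- The paragraph under the table repeats the rule without a number of weeks: "If no tumor assessments are performed unless patients die within two visits of baseline visit".
- The adjacent row censors at the last evaluable scan when a "Patient progresses or dies immediately after two or more consecutive missed visits".

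A further row of Table 6 makes death without progression an event on the date of death. The SAP gives no order of precedence among the rows.

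Table 6 does not define baseline. SAP Section 7.1 does: "Baseline evaluations or events will be defined as evaluations or events that occur before the date and time of the first dose" of study drug, with evaluations at the time of first dose also allowed and the one closest to first dose used. The protocol's schedule has a "Screening Period Within 28 Days prior to first dose", and SAP Section 4.1 agrees: "From the day of informed consent form (ICF) signature (up to 28 days before first dose) to the day before the first dose".

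**The concern.** The exception is there so that a patient who deteriorates and dies before being scanned is not lost from the analysis. Its time limit, however, is counted from a different date than PFS and the scans. A baseline scan is taken on or before first dose, so counting 12 weeks from it shortens the on-treatment time that the exception covers, by an amount that depends on when in screening the scan was booked. That has nothing to do with the drug.

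The patients concerned are early failures. Censoring them at Day 1 takes them out of the risk set from the start, and the reason for the missing scan may well be the decline that led to death. PFS is a secondary endpoint in Parts A2 and B. If Part B randomizes two dose levels, with about 20 patients each, Protocol Section 4.2.2 compares them on the totality of efficacy and safety data.

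**Working it through.** **Inputs.** Scan interval 42 days, window ±7 days, counted from C1D1 (Protocol Table 1). In Parts A2 and B, C1D1 is the first dose, because the PK lead-in applies to Part A1 only. Limit of the exception: less than 12 weeks, or 84 days, from baseline (SAP Table 6). Baseline scan: s days before first dose, s from 0 to 28 (Protocol Table 1, SAP Sections 4.1 and 7.1).

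**Step 1: the SAP's own figure.** Two visits × 42 days = 84 days = 12 weeks. This reproduces the 12 weeks in Table 6, but only when counted from C1D1 and without the scan window.

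**Step 2: when a second scan has been missed.** The first window runs from week 5 to week 7. The second runs from 84 − 7 = 77 days to 84 + 7 = 91 days, that is, week 11 to week 13. If a scan counts as missed once its window has closed, nobody has missed two before week 13.

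**Step 3: when the exception ends.** With the limit run from the baseline scan, a death counts only before day 84 − s after first dose, which is week 12 − s/7. The gap to the close of the second window is 91 − (84 − s) = 7 + s days.

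| Baseline scan, days before first dose (s) | Exception ends, days after first dose | Week | Gap to week 13 |
|---|---|---|---|
| 0 | 84 | 12 | 7 days |
| 7 | 77 | 11 | 14 days |
| 14 | 70 | 10 | 21 days |
| 21 | 63 | 9 | 28 days |
| 28 | 56 | 8 | 35 days |

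If baseline means the date of first dose, the result is the top row: a gap from week 12 to week 13.

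**Step 4: an example.** Two patients die 63 days after first dose with no post-baseline scan. Each has missed only the week-6 scan. If the baseline scan was 1 day before first dose, the death is 64 days from baseline and is an event. If it was 27 days before, the death is 90 days from baseline, past 84, and the Table 6 limit censors the patient at Day 1.

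**Step 5: effect on the estimate (assumed counts).** Take 20 patients, 7 PFS events by 3 months and no other censoring. Seven is roughly what an exponential curve with a 4.5-month median gives: 20 × (1 − 0.5^(3/4.5)) = 7.4. That median is the middle of the 4 to 5 months that Protocol Section 2.1.1 cites for chemotherapy after osimertinib. It is not a figure for TAS3351.

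- All 7 counted: 1 − 7/20 = 65.0%.
- One censored at Day 1: 1 − 6/19 = 68.4%.
- Two censored at Day 1: 1 − 5/18 = 72.2%.

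In general, with k events among n patients, censoring one of them changes the estimate after that death by k/n − (k − 1)/(n − 1) = (n − k)/[n(n − 1)], which is never negative. Here it is 13/380 = 3.4 points. Before the death the curve can be slightly lower, because the risk set is one smaller.

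**Step 6: how many patients (assumed survival).** With exponential survival and median OS of 6, 12 or 18 months, the chance of dying between weeks 8 and 13 is 10.1%, 5.8% or 4.0%, or 2.0, 1.2 or 0.8 deaths per 20 patients. Between weeks 12 and 13 it is 1.9%, 1.1% or 0.8%. Under these assumptions the expected number affected is lower than this, because it includes only deaths without an evaluable scan and, for most of the gap, only patients scanned early in screening.

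**The case against.** **The week-8 limit is not the plain reading.** Two visits equal 12 weeks only when counted from C1D1, so the parenthesis in Table 6 may have been meant from first dose. The row also covers patients with no baseline scan, who have no scan date to count from. This stands as a limit on size: week 8 needs a scan 28 days before first dose and baseline read as the scan date. SAP Section 7.1 supports that reading, but Table 6 does not state it. A reader might infer that all scan-less deaths from week 8 to week 13 are censored; the documents do not support that.

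**The text under the table has no 12-week limit.** Counted in scheduled visits, both deaths in the example would be events. This is correct, and it means that table and text give different answers for the same patient.

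**The general death row may prevail.** If it did, the exception for early deaths would do nothing, since every such death would already be an event. The row makes sense only if it overrides the general one. The SAP should still say so.

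**Thirteen weeks is a convention.** The SAP does not say when a visit counts as missed. The last week of the gap rests on allowing the protocol's 7-day window; without it, 12 weeks from first dose would match two visits. Patients who stop treatment without progression are scanned every 9 weeks, so no fixed limit equals two scheduled scans for everyone. Both points stand, but neither defends counting from baseline.

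**The effect is small.** A 3.4-point shift compares with a standard error of √(0.65 × 0.35/20) = 10.7 points, and the number of affected patients is assumed. A reader might infer that the Part B result or dose choice is compromised. The documents do not support that: the primary endpoint is ORR, which this rule does not touch, OS counts every one of these deaths, and all deaths are tabulated.

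**Conclusion.** The point holds in a limited form. Table 6 ends the exception at week 12 − s/7 after first dose if baseline is the screening scan, and at week 12 if baseline is first dose. Deaths from then until week 13, a gap of 1 to 5 weeks, can be censored at Day 1 after at most one missed scan, against the two-visit standard of the adjacent row and without support from the text below the table.

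The upper end of the gap assumes a scan 28 days before first dose; the lower end assumes that a scan is missed only once its window has closed. Few patients are likely to be affected, and PFS is secondary and descriptive, with no formal hypothesis (Protocol Section 12.2). The direction is one-sided: from the date of the death onward, PFS can only be raised. The shift from 65% to 68% is an illustration under assumed counts, not a forecast.

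A reader might extend the finding to Part C. This SAP covers Parts A and B only, so nothing can be said about the rule that Part C will use.

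**What to change.** In Table 6 and in the paragraph below it, use one rule anchored on first dose: a patient with no evaluable baseline scan, or no evaluable post-baseline scan, is censored at the date of first dose, unless the patient dies within 13 weeks of first dose (two scheduled scans plus 7 days), in which case PFS is an event on the date of death. State that this row takes precedence over the general row for death without progression. The new anchor also works for patients without a baseline scan.

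The cost is a short change of wording in two places and a simple programming change, with no new data. The downside is that reported PFS may be slightly less favorable.

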5.5.7. Overall Survival (OS)

Overall survival is defined as the time from the date of first dose to the date of death due to any cause. For patients without documentation of death, the OS will be censored at the last contact date the patient was known to be alive. [Table 7](#) summarizes event and censoring rules for OS.

Table 7: Event and Censoring Rules for OS

Event/Censor	Decision	Date of event or censor to consider for analysis
Death	Event	Date of death
Patient alive without documented death	Censor	Date of last contact*

* Maximum date among completed dates relative to patient's information

In the absence of death confirmation or for patients alive as of the data cut-off date, survival time will be censored at the date of patient last known alive, or the data cut-off date, whichever is earlier. The patient last known alive is defined as the latest among dates recorded on eCRF.

Secondary Analysis in Part A (Patients in part A2 only), B

The Kaplan-Meier method will be used to estimate the median and percentile with the 2-sided 95% CI calculated using the Brookmeyer and Crowley method.

Kaplan-Meier plot will be provided.

End of safety follow-up data, survival follow-up data, and post study treatments data will be presented in by-patient listings.

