5.6. Withdrawal from the Study

A patient will be withdrawn from all study interventions and assessments (ie, discontinued from the study without follow-up) for any of the following reasons:

1. Death
2. Patient withdrawal of consent to further follow-up assessments, irrespective of the reason.
3. Lost to follow-up
 - A patient will be considered lost to follow-up if he/she repeatedly fails to return for scheduled visits and is unable to be contacted by the study site.
 - The following actions must be taken if a patient fails to return to the clinic for a required study visit:

- The site must attempt to contact the patient and reschedule the missed visit as soon as possible, counsel the patient on the importance of maintaining the assigned visit schedule and ascertain whether or not the patient wishes to and/or should continue in the study.
- Before a patient is deemed lost to follow-up, the Investigator or designee must make every effort to regain contact with the patient (when possible, 3 telephone calls, and [if necessary] a certified letter to the patient's last known mailing address, or local equivalent methods). These contact attempts should be documented in the patient's medical records.
- Should the patient continue to be unreachable, he/she will be considered to have withdrawn from the study.

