5.3. Study Population

5.3.1. Patient Disposition

Patients may be pre-screened for *EGFR* C797S status prior to the screening. These data will be captured in EDC screening folder. The number of patients who are pre-screened and their gender, *EGFR* status will be summarized and listed.

The total number of patients screened will be presented. Number of screen failures, number of patients not treated with study drug along with reason will be tabulated. Number of patients who discontinued treatment/study along with corresponding primary reason will be tabulated. Number of patients ongoing at time of data cutoff, and for part A1, number of patients who are DLT evaluable per dose level will also be tabulated.

Listings for informed consent patients will be provided showing each patient's informed consent date with protocol amendment version, date of re-consent, if available, reason for not being treated with study drug, first and last dosing date, date of study ending and primary reason for discontinuation of treatment and end of study. A listing to present DLT evaluable patient disposition for patients in DLT evaluable population of part A1 will be provided. A listing for patients not treated will also be provided, showing each patient's race, gender, age, and consent date.

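### SAP 5.5.7 gives conflicting censoring dates for overall survival, and the one worded as the definition does not require evidence that the patient was alive

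*SAP*

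**What the plan says.** SAP 5.5.7 (Overall Survival) states the censoring date in three places.

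- **Opening paragraph:** for patients without a documented death, "the OS will be censored at the last contact date the patient was known to be alive".
- **Table 7:** the table body names the date of last contact, but its footnote explains this as "Maximum date among completed dates relative to patient's information".
- **Closing text:** "survival time will be censored at the date of patient last known alive, or the data cut-off date, whichever is earlier". The next sentence fixes the meaning: "The patient last known alive is defined as the latest among dates recorded on eCRF".

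The opening paragraph requires evidence of life. The footnote and the closing definition do not.

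Three other places bear on this. SAP 5.3.1 plans a per-patient listing that includes "date of study ending and primary reason for discontinuation of treatment and end of study". Protocol 5.6 says "A patient will be considered lost to follow-up if he/she repeatedly fails to return for scheduled visits and is unable to be contacted", requires contact attempts before that status is given, and adds: "Should the patient continue to be unreachable, he/she will be considered to have withdrawn from the study". For Parts A2 and B, the survival-status row of Protocol Table 1 reads "Every 3 months (±2 weeks); collect also further anticancer therapies".

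**The concern.** For most patients all the wordings give the same date. They can part for a patient who stops responding. The last real contact is one date, and the date on which the site closes the patient's participation may be a later one. A maximum over all eCRF dates picks the later date, although nobody knew then whether the patient was alive and a death in between would probably not have been recorded.

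The added time is event-free by construction, so any error runs in one direction. The SAP is stricter for its other time-to-event endpoints: Tables 5 and 6 censor duration of response and progression-free survival at the last evaluable scan. Only OS lacks an evidence condition in its operative definition.

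At stake are the OS curves and medians for Part A2 (about 20 patients) and Part B (about 20 per cohort), and the risk that two programmers following the same section produce different results.

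**Working it through.** **1. No plan figure to reproduce.** The documents state no OS median, event count, loss rate or power.

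**2. The wordings side by side.** Take a patient with last contact at time L, no recorded death, and a later study-ending date L + g on the eCRF, before data cut-off. The opening sentence gives L. The footnote and the closing definition give L + g. The cut-off cap does not help, because L + g is earlier than the cut-off.

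**3. Direction.** The Kaplan-Meier estimate is S(t) = Π(1 − d/n) over death times. Moving a censoring date later adds no death and can only raise n at later death times, so S(t) cannot fall. Illustration with assumed numbers: one death with 9 at risk gives 1 − 1/9 = 0.889. With the lost patient still counted, it gives 1 − 1/10 = 0.900. If S was 0.60 before, it becomes 0.533 or 0.540.

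**4. Size, by simulation.**

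From the documents: N = 20 (one Part B cohort, or Part A2) and N = 40 (Part B), and the 6-month minimum follow-up in SAP 4.3.2.

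Assumed: exponential OS with a 12-month median; 12 months of uniform accrual; 5%, 10% or 20% of patients assigned a loss date, uniform over their follow-up; no death recorded after loss; a gap g of 1, 3 or 6 months or carry to cut-off, always capped at cut-off; 2,000 replicates. Assigned patients who die before their loss date count as deaths.

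Each cell shows censoring at last contact → literal eCRF rule, with the difference in brackets.

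| Loss, gap | Median OS in months, N = 20 | Median OS in months, N = 40 | 12-month OS, rise in points (N = 20 / 40) |
|---|---|---|---|
| 5%, 1 mo | 11.99 → 12.02 (0.03) | 11.90 → 12.00 (0.10) | 0.1 / 0.1 |
| 5%, 3 mo | 12.07 → 12.30 (0.23) | 11.98 → 12.09 (0.11) | 0.5 / 0.4 |
| 10%, 1 mo | 12.06 → 12.18 (0.12) | 12.10 → 12.18 (0.08) | 0.3 / 0.3 |
| 10%, 3 mo | 12.19 → 12.43 (0.24) | 11.86 → 12.18 (0.32) | 0.9 / 0.8 |
| 20%, 3 mo | 12.20 → 12.79 (0.59) | 12.03 → 12.75 (0.72) | 1.7 / 1.8 |
| 20%, 6 mo | 12.09 → 13.23 (1.14) | 12.11 → 13.44 (1.33) | 3.1 / 3.1 |
| 20%, to cut-off | not run | 12.06 → 13.80 (1.74) | – / 4.4 |

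In every simulated dataset, 6- and 12-month survival under the literal rule was equal to or above the value with censoring at last contact.

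A repeat with 8,000 replicates gave 0.03 to 0.3 months for the first four rows, about 1.2 for 20% with 6 months, and 1.8 to 1.9 for carry to cut-off. The upper figures therefore carry simulation error of about 0.2 months.

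**5. Scale.** Under the same assumptions with N = 20 and no loss, the observed median, where reached, lies between about 5 and 16 months in 95% of trials. It is not reached in about a quarter of them.

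**The case against.** The strongest reply is that the section already states the standard rule twice, in its opening sentence and in the body of Table 7. On that view the closing sentence is loose shorthand that a sensible programmer would read in that light. This stands in part: the defect is a contradiction, and the bias arises only if the closing words are followed literally. But those words are framed as the definition and the footnote supports them, so a literal reading is reasonable. SAP 7.4 sends other handling rules to a separate document, which cannot be assumed to override an explicit definition here.

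Several further points stand and limit the finding:

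- **Study-ending date.** No document says whether, for a lost patient, this is the last contact or the day loss was declared. That it falls later, and is held on the eCRF, is an inference from SAP 5.3.1 and Protocol 5.6.
- **Few patients are affected.** A documented death still counts at its own date, and Protocol Table 12 allows family to be contacted for survival status.
- **Gap length.** Protocol 5.6 sets no timetable. On treatment, visits come at least every 21 days, so loss would be noticed early. In survival follow-up, quarterly contact makes a gap of some months plausible but does not establish it.
- **Low consequence.** OS is secondary, Protocol 12.2 states no formal hypothesis, and the plausible shift is small beside the sampling variation of a 20-patient cohort.

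A reader might also infer that OS in Part C is affected, or that the Part B dose with more loss will look better because lost patients fare worse. The documents support neither. This SAP covers Parts A and B only, and nothing in either document describes the prognosis of lost patients or unequal loss between doses.

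**Conclusion.** The point holds as an internal contradiction with an over-broad operative definition. It does not show that patients will be censored at administrative dates, or that survival will be overstated. If the closing definition is applied literally, the error can only be upward, and it affects only patients in Parts A2 and B who are lost with no recorded death and have a later eCRF date before cut-off.

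The direction follows from the estimator. The size rests wholly on assumed loss rates, gaps and a 12-month median: about 0.03 to 0.3 months in the median, and under 1 point in 12-month OS, at 5-10% loss with a 1-3 month gap. It rises to about 1.1 to 1.7 months and 3 to 4 points at 20% loss with a 6-month gap or carry to cut-off. The response rate does not depend on this rule. The wording should be corrected because the correction is cheap and removes an ambiguity, not because a main conclusion of the study is at risk.

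**What to change.** Replace the closing definition and the Table 7 footnote in SAP 5.5.7 with one rule that matches the opening sentence, for example:

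*Last known alive is the latest eCRF date, on or before data cut-off, that documents the patient alive: a visit, assessment, dose, sample collection, scan, adverse event onset, or survival contact with status alive. Study-end dates, dates on which loss to follow-up was determined, failed contact attempts, and reporting dates are excluded.*

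The existing cap at data cut-off stays. If the SAP for Part C reuses this section, it should carry the corrected wording.

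The cost is one sentence, one footnote and one derivation, with no new data collection. The downside is that OS may look slightly less favourable than under the literal rule.
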